Clinical Study Protocol

Dotarem® for Myocardial Perfusion Cardiovascular Magnetic Resonance

Principal Investigators: U. [name]

Medical University of South Carolina
Department of Radiology and Radiological Science
[name]
[name]

CONFIDENTIALITY STATEMENT

This document is the confidential property of Medical University of South Carolina, Radiology Department. No Part of it may be transmitted, reproduced, published or used by other persons without the permission of the Principal Investigator.

Dotarem® Evaluation for Myocardial Perfusion Cardiovascular Magnetic Resonance

Table of Contents

A. SPECIFIC AIMS	3
B. BACKGROUND AND SIGNIFICANCE	3
C. PRELIMINARY STUDIES	3
D. RESEARCH DESIGN AND METHODS (including data analysis)	4
D.1 Image acquisition	4
D.2 Image analysis	5
D.3 Statistical Methods / Sample Size Justification	5
E. PROTECTION OF HUMAN SUBJECTS	5
E.1 RISK TO THE SUBJECTS	5
E.1.a Human Subject Involvement and Characteristics	5
E.1.b Sources of Materials	7
E.1.c Potential Risks	7
E.2 ADEQUACY OF PROTECTION AGAINST RISKS	8
E.2.a Recruitment and Informed Consent	8
E.2.b Protection against Risk	9
E.3 POTENTIAL BENEFITS OF THE PROPOSED RESEARCH TO THE SUBJECTS AND OTHERS	9
E.4 IMPORTANCE OF THE KNOWLEDGE TO BE GAINED	9
E.5 SUBJECT SAFETY AND MINIMIZING RISKS (Data and Safety Monitoring Plan)	10
F. FACILITIES AVAILABLE	10
G. REFERENCES	10

A. SPECIFIC AIMS

The overall goal of this study is to investigate the signal intensity and relaxation rate characteristics of gadoterate meglumine (Dotarem, Guerbet, USA) enhanced myocardium during rest and stress perfusion cardiovascular magnetic resonance (CMR) compared to gadobutrol (Gadavist) to prove that Dotarem provides constantly high myocardial relaxation necessary for accurate quantitative perfusion evaluation. Within this overall goal, the following specific aims will be pursued:

- **Aim 1:** To test the hypothesis that the signal intensity enhancement during Dotarem myocardial stress/rest perfusion is relatively constant, providing linear and stable enhancement in the myocardium, and is not inferior compared to gadobutrol (Gadavist).
- **Aim 2:** To test the hypothesis that the relaxation rate enhancement during Dotarem myocardial rest perfusion is uniform in the myocardium.

B. BACKGROUND AND SIGNIFICANCE

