Stress perfusion imaging is indicated in symptomatic patients suspected of coronary artery disease (CAD) with low or intermediate cardiovascular risk and typical/atypical chest pain or angina-equivalent symptoms, as well as in asymptomatic patients with high cardiovascular risk profiles, such as diabetics, or in patients with known CAD during follow-up.¹ Myocardial perfusion by CMR was introduced approximately two decades ago.² Compared with SPECT, which uses a radioisotope that is actively taken up by the myocytes to depict myocardial perfusion, CMR evaluates the first pass of an extracellular contrast agent (CA) within the myocardium. Whereas the stress protocol used for both methods is similar, CMR offers the benefit of superior spatial and temporal resolution, and SPECT is associated with the negative effects of exposure to ionizing radiation.^{3, 4} Although, several studies proved that stress perfusion CMR outperforms stress perfusion SPECT⁵⁻⁷, the quantitative evaluation of myocardial blood flow by CMR is still a challenging topic due to, for example, the non-linear signal intensity changes and the different relaxation rate enhancements caused by the various gadolinium-based CAs⁸⁻¹⁰, representing a major limitation to the widespread use of the technique in clinical practice.

Dotarem, a macrocyclic agent with fast clearance kinetics, has the highest thermodynamic stability among the currently approved clinical contrast agents.¹¹ This high stability is due to its molecular structure, which provides a significantly reduced dissociation rate (i.e. Release of free gadolinium ions) compared to other agents.¹¹ While the *in vitro* relaxivity ($3.4 \text{ mm}^{-1}\text{s}^{-1}$)¹² of Dotarem is comparable to other agents, we suggest that its high stability and extremely low dissociation rate provide constant signal intensity and relaxation rate enhancement during myocardial perfusion CMR, improving the accuracy and reliability of quantitative perfusion analysis.

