The efficacy of Dotarem enhanced late gadolinium enhancement (LGE) imaging has been investigated and compared to gadobutrol (Gadavist, Bayer, Germany) to visualize and quantify myocardial scar.¹³ However, a similar comparison for the assessment of myocardial ischemia by CMR myocardial perfusion – an even more crucial step in a clinical CMR protocol – would further strengthen the value of Dotarem in cardiovascular imaging. While LGE is able to visualize irreversible myocardial injury, myocardial perfusion imaging has the ability to depict reversible ischemia that can potentially be treated by coronary intervention.

C. PRELIMINARY STUDIES

Our research group consists of clinical and research faculty who have extensive experience and a substantial publication record related to contrast enhanced cardiac MRI and contrast agent characterization.¹⁴⁻¹⁸ In a previous research project, our team developed an image analysis technique (detailed in Section D) that we will use in Aim 2 to investigate the relaxation profile of Dotarem.¹⁶

D. RESEARCH DESIGN AND METHODS (INCLUDING DATA ANALYSIS)

D.1 IMAGE ACQUISITION

This prospective study will include a total of 90 patients (Aim 1 + Aim 2) who present to the MUSC Radiology Department for a clinically indicated cardiac MRI scan over a 2-year period. Patients will be imaged using a state of the art 1.5T scanner (MAGNETOM Avanto, Siemens Healthcare, Erlangen, Germany) system.

Aim 1: In this specific aim, a total of **60 patients** referred for a clinically indicated stress myocardial perfusion MRI scan out of concern of suspected myocardial ischemia will be included. Patients will be scanned using a **standard clinical contrast-enhanced stress perfusion protocol** (regadenoson 0.4mg bolus) detailed in Figure 1. Patients will be randomized into two groups prior to patient consenting: **Group 1 (n=30)** will receive the **clinically approved gadoterate meglumine** (Dotarem, 0.1mmol/kg) as contrast agent for their clinical perfusion study, while **Group 2 (n=30)** will receive the **clinically approved gadobutrol** (Gadavist, 0.1mmol/kg) as contrast agent. The contrast agents will be administered at a flow rate of 5.0 ml/s for both groups. In this study aim, all imaging protocols will comply with standard of care and only the perfusion data will be post-processed and analyzed.

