Aim 2: In this specific aim, a total of **30 patients** referred for a clinically indicated contrast enhanced cardiac MRI will be included. These patients will undergo a **clinical viability cardiac MRI protocol** with the administration of **gadoterate meglumine** (Dotarem, 0.1mmol/kg), except that a **prototype MRI T1 mapping pulse sequence** will be used to acquire equilibrium T1 maps during the first pass of the contrast agent. This first pass perfusion step will be performed in rest, no stress agent will be administered. The rest perfusion acquisition is part of the standard protocol, however, we will use this prototype pulse sequence for research purposes.

[figure not shown]

Figure 1 – MRI protocols

D.2 IMAGE ANALYSIS

In Aim 1, we will generate signal intensity-time curves from the perfusion data and evaluate the characteristics of signal intensity changes and absolute myocardial blood flow using the MASS Research Software (LUMC, Leiden, Netherlands). The signal characteristics will be compared between the two contrast groups. Image quality will also be subjectively rated by multiple independent observers.

In Aim 2, we will generate equilibrium T1 maps based on the pre-contrast T1 and repeated inversion recovery images during the perfusion of the CA. This technique allows the calculation of the post-contrast T1 at every phase during the first-pass perfusion of the CA. The uniformity of T1 and R1 (inverse T1) will be evaluated using the MASS Research Software.

D.3 STATISTICAL METHODS / SAMPLE SIZE JUSTIFICATION

All analyses and graphs will be performed by using commercially available software (MedCalc version 12.7.2; SPSS version 21). Descriptive statistics will be provided as mean \pm standard deviation (SD) for continuous variables and absolute and relative frequencies for categorical variables. Normal data distribution will be assessed with a Kolmogorov-Smirnov test. For each group, comparisons of patient characteristics will be performed by using the χ^2 test for categorical variables and t-test or Mann-Whitney-U-test for continuous variables as appropriate. Subjective image quality scores will be compared using the χ^2 test with the Yates continuity correction for categorical variables and inter-observer agreement for image quality will be calculated using Cohen kappa statistics and interpreted as follows: ≤ 0.20 slight or poor agreement, $0.20-0.40$ fair agreement, $0.40-0.80$ moderate agreement, ≥ 0.80 excellent agreement.

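### Aim 1 hypothesises linear enhancement, but as described it analyses signal-time curves at one dose per arm, so linearity cannot be identified from its data

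*Combined protocol and SAP*

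**What the plan says.** Section A states, as part of the Aim 1 hypothesis, that Dotarem's signal enhancement at stress and rest is relatively constant, "providing linear and stable enhancement in the myocardium", and that it "is not inferior compared to gadobutrol (Gadavist"). The variable in which enhancement should be linear is not named. Section B shows the intended sense: among the obstacles to quantifying blood flow by CMR it lists "the non-linear signal intensity changes and the different relaxation rate enhancements" of the various agents.

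For the Aim 1 analysis, Section D.2 says "we will generate signal intensity-time curves from the perfusion data and evaluate the characteristics of signal intensity changes and absolute myocardial blood flow", using named research software. It then compares signal characteristics between the groups and adds subjective image quality. Section D.1 limits the Aim 1 analysis: "only the perfusion data will be post-processed and analyzed". Each Aim 1 arm has one dose level (0.1 mmol/kg) and the same injection rate, with 30 patients randomised to each agent.

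T1 and R1 appear only in Aim 2, where "we will generate equilibrium T1 maps based on the pre-contrast T1 and repeated inversion recovery images". Aim 2 covers 30 other patients, given Dotarem only, at rest only, and the stated analysis is uniformity. Section D.3 names tests for patient characteristics, image quality and observer agreement. It names none for signal, linearity or blood flow.

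**The concern.** Linearity is a statement about two quantities: signal, and the amount of contrast (or R1) that produces it. Aim 1 as described records the first and not the second. If the plan is followed exactly, smooth, stable or similar curves could be read as support for linear enhancement, although they carry no information on it. This matters because Section A's overall goal is to prove that Dotarem gives what accurate quantitative perfusion needs, and Section B names signal non-linearity as an obstacle to that.

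The same gap limits what the blood-flow comparison can mean. Flow is derived from the signal curves, and the text describes no conversion to R1 or concentration. A between-arm difference could therefore reflect how signal responds to each agent. Agreement between arms would not show that either is accurate.

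**Working it through.** The plan states no figure for linearity, so there is none to reproduce. The check has three steps. All model values are assumptions except Dotarem's relaxivity, 3.4, from Section B (read as per mM per s).

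**Step 1. Can a signal-time curve identify linearity?** Assume a saturation-recovery signal S = 1 − exp(−TS × R1), with R1 = R10 + r × C. Write x = TS × r × C. The enhancement is exp(−TS × R10) × (1 − exp(−x)). A linear response with the same initial slope is exp(−TS × R10) × x. For any saturating curve with concentration C(t), define C′(t) = (1 − exp(−x(t))) / (TS × r). A linear response driven by C′(t) then gives exactly the same signal at every time. At TS = 0.10 s and a peak of 1.00 mM, x = 0.34 and C′ peaks at 0.2882 / 0.34 = 0.85 mM. The numerical difference between the two signal curves was below 1e-16. Only a measure of concentration or R1 could separate them. More patients or cleaner curves would not.

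**Step 2. How far from linear could myocardial signal be?** The signal-to-linear ratio is (1 − exp(−x)) / x, taken at r = 3.4 and C = 1 mM:

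| TS (s) | x | Ratio | Shortfall |
|---|---|---|---|
| 0.05 | 0.17 | 0.920 | 8% |
| 0.10 | 0.34 | 0.848 | 15% |
| 0.15 | 0.51 | 0.783 | 22% |

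Saturation also compresses differences in peak signal between agents. At TS = 0.10 s and 1 mM, a comparator with 1.5 times the relaxivity has x = 0.51. Its peak enhancement ratio to Dotarem is 0.3995 / 0.2882 = 1.39, not 1.5.

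**Step 3. What would this do to flow between arms?** Take identical true flow and use the ratio of peak myocardial to peak blood enhancement as a simple stand-in for uncorrected flow. Further assumptions are pre-contrast T1 of 1.0 s (myocardium) and 1.5 s (blood), blood peak 2 to 8 mM, myocardial peak 12% of blood, and TS 0.05 to 0.15 s. The pre-contrast terms cancel between agents. One case worked through, with TS = 0.10 s, blood 5 mM and myocardium 0.6 mM:

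- Dotarem: (1 − exp(−0.204)) / (1 − exp(−1.7)) = 0.1845 / 0.8173 = 0.2258
- Comparator at 1.5 times the relaxivity: (1 − exp(−0.306)) / (1 − exp(−2.55)) = 0.2636 / 0.9219 = 0.2859
- Ratio: 0.2859 / 0.2258 = 1.27

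Over the whole grid:

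| Comparator relaxivity relative to Dotarem | Apparent flow ratio, comparator to Dotarem |
|---|---|
| 1.0 | 1.00 |
| 1.1 | 1.01 to 1.07 |
| 1.5 | 1.07 to 1.32 |

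The documents give no relaxivity for gadobutrol, so this is a range and not a prediction.

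**The case against.** Several objections have force, mostly on blood flow.

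- **Randomisation.** A reader might infer that no between-agent flow difference can be concluded at all. The documents do not support that. Aim 1 randomises 30 to 30 at equal dose and injection rate, so true flow is balanced in expectation and a difference in *measured* flow can be attributed to the agent. This is subject to precision (95% half-width about 2.00 × √(2/30) = 0.52 SD) and to allocation preceding consent. What stays out of reach is a true flow difference, or which agent quantifies better.
- **No flow hypothesis.** Section A hypothesises nothing about a flow difference. Flow is one evaluated quantity in D.2. Nor does the plan offer Aim 2 as a test of linearity.
- **Silence is not absence.** A reader might infer that flow will be computed from uncorrected signal. The text only leaves conversion undescribed. Figure 1 was not available in the text reviewed, the software may convert internally, and the reference list includes work on non-linear signal correction.
- **Size.** Under the Step 1 model, pairing 1 mM in myocardium with 5 mM in blood overstates the myocardium-to-blood ratio 1.4 to 2.2 fold (0.920/0.674 to 0.783/0.362). It is tempting to cite this as the harm, but it is a bias within one agent that can affect both arms. Section B calls Dotarem's relaxivity comparable to that of other agents, which on the plan's own premise points to the low end of the Step 3 range.
- **Linear in time.** The rising part of the curve could be assessed for straightness. That answers a different question: upslope shape also depends on bolus delivery and flow, and Section B uses non-linearity of the signal response.

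None of these supplies a concentration, R1 or dose axis for Aim 1, so the linearity point stands.

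**Conclusion.** The concern holds for linearity. Section A makes it part of a hypothesis, and the analysis described in D.1 and D.2 cannot identify it under any result. Aim 2 does not close the gap, since gadobutrol never receives an R1 measurement and neither agent receives one at stress.

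For blood flow the point is a limit on interpretation: between-arm results concern measured flow, and equal measured flow would not establish accuracy, since both arms could be biased alike. The illustrative sizes (8% to 22% myocardial shortfall at 1 mM; flow ratios from 1.00 to 1.32) rest on the assumed signal model, saturation times, concentrations and relaxivity ratios. The identifiability result needs none of those values. It depends only on the missing axis. No number stated in the plan is wrong. The change is worth making because it alters what the trial may conclude.

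**What to change.** 1. In Section A, delete 'linear' from the Aim 1 hypothesis, and do not use it in the Aim 1 conclusion.
2. Restate Aim 1 as what the curves measure: relative myocardial signal enhancement at stress and rest, its variability, and its comparison with gadobutrol. Note that saturation compresses between-agent differences in peak signal, which makes non-inferiority on that measure easier to show. The non-inferiority margin, which the plan does not give, is a separate matter that this rewording does not settle.
3. In D.2, state how signal is handled before flow is calculated. If the existing acquisitions and software allow it, apply the same signal-to-R1 or signal-to-concentration method in both arms, with each agent's own relaxivity where concentration is used. This is conditional because the text does not show that Aim 1 acquires a baseline T1.
4. Otherwise, report between-arm results as differences in measured flow only, not as true flow differences or as evidence of either agent's quantification accuracy.

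The rewording and the fallback in item 4 need no new patients or scans. Conversion costs analysis time where the inputs exist. The downside is that the trial gives up a linearity claim that its data could not support.

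### Aim 1 claims non-inferiority of Dotarem to gadobutrol, but the plan sets no signal parameter, direction, margin or confidence-interval rule to test it

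*Combined protocol and SAP*

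**What the plan says.** - **Section A, Aim 1** states a hypothesis to be tested, in two parts. The first part describes Dotarem on its own: "signal intensity enhancement during Dotarem myocardial stress/rest perfusion is relatively constant, providing linear and stable enhancement in the myocardium". The second part of the same hypothesis is comparative: "and is not inferior compared to gadobutrol (Gadavist").
- **Section B** gives the rationale, that Dotarem's stability should "provide constant signal intensity and relaxation rate enhancement during myocardial perfusion CMR".
- **D.1, Aim 1** makes this a randomized comparison: "Patients will be randomized into two groups", 30 receiving Dotarem and 30 receiving gadobutrol.
- **D.2** plans to "evaluate the characteristics of signal intensity changes and absolute myocardial blood flow", and on the comparison says only: "The signal characteristics will be compared between the two contrast groups".
- **D.3** names between-group tests for two kinds of data. For baseline data, "comparisons of patient characteristics will be performed by using the" chi-square test, or the t-test or Mann-Whitney test. For reader scores, "Subjective image quality scores will be compared using the" Yates-corrected chi-square test. It also gives a normality test and Cohen's kappa. Signal intensity and myocardial blood flow are not mentioned, and despite its heading the section contains no sample size calculation.

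**The concern.** A non-inferiority claim needs a defined outcome, a direction that counts as worse, a margin, and a rule for comparing a confidence limit with that margin. The plan has none of these for signal intensity.

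Two things follow. First, the only analytic models in D.3 are difference tests. If one were carried over to signal intensity, a significant deficit would count against the hypothesis, but a non-significant result would show only that no difference was detected, and could be reported as non-inferiority. Second, the parameter, the condition (stress or rest), the direction and the margin could all be chosen after the data are seen. The claim at stake is a stated hypothesis of the study's only randomized comparison, and section A gives proof of a Dotarem property as the overall goal.

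**Working it through.** **1. What non-inferiority needs, against what the plan gives**

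| Element | In the plan |
|---|---|
| Primary signal parameter | None. D.2 names signal-intensity characteristics and absolute blood flow without ranking them |
| Condition | Aim 1 covers both stress and rest; neither is primary |
| Direction that is worse | Not stated. For a height measure, lower is worse; for variability or non-linearity, higher is worse |
| Margin | None |
| Alpha and confidence-interval rule | None |
| Test assigned to signal intensity | None |

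The one missing figure is captioned as the MRI protocols and would not be expected to hold a statistical rule.

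**2. The plan's own figure**

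The 30 per arm in D.1 cannot be reproduced, because no margin, effect, SD, alpha or power is given. Solving backwards with the normal approximation at two-sided 5% and 80% power:

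d = (1.960 + 0.842) × √(2/30) = 2.802 × 0.2582 = 0.723 SD.

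The documents state no such value.

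**3. What 30 per arm can support (illustration)**

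Assumptions, none of them from the documents: independent groups, equal SD, t-test, two-sided 5% (one-sided 2.5% for non-inferiority), results in SD units. Only n = 30 per arm comes from D.1.

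- Standard error: √(2/30) = 0.2582 SD, with 58 degrees of freedom.
- Critical value: t(0.975, 58) = 2.0017.
- 95% CI half-width: 2.0017 × 0.2582 = 0.517 SD.

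*Difference test when Dotarem is truly worse by δ* (noncentral t, noncentrality δ/0.2582):

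| True deficit | Noncentrality | Significant deficit | Non-significant |
|---|---|---|---|
| 0.3 SD | 1.162 | 0.207 | 0.792 |
| 0.5 SD | 1.936 | 0.478 | 0.522 |

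*Confidence-interval rule when there is no true difference.* Power at margin M is the probability that a noncentral t with noncentrality M/0.2582 exceeds 2.0017. This is the same calculation as the significant-deficit column, read for a different purpose:

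| Margin | Power |
|---|---|
| 0.3 SD | 0.207 |
| 0.5 SD | 0.478 |
| 0.75 SD | 0.815 |

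Power reaches 80% at a margin of 0.736 SD. The 0.723 SD in step 2 is smaller only because it uses the normal approximation.

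**4. Effect of unusable scans (loss rates assumed)**

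| Per arm | Half-width | Power at 0.5 SD | Margin for 80% power |
|---|---|---|---|
| 30 | 0.517 SD | 0.478 | 0.736 SD |
| 27 (10% lost) | 0.546 SD | 0.438 | 0.777 SD |
| 24 (20% lost) | 0.581 SD | 0.396 | 0.826 SD |

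The figures are the same whichever direction is worse. They are not proposed margins.

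**The case against.** - **Direction.** What must not be inferior is the signal enhancement itself, which reads most naturally as lower being worse, and the overall goal speaks of high relaxation. This has some force: the direction is less open than the table alone suggests. But the goal concerns relaxation, Aim 1 also stresses constancy and linearity, and no direction is fixed.
- **Misuse is conjecture.** Nothing says a non-significant test will be read as non-inferiority, or that the baseline tests will be applied to signal intensity. That is right, so the 52% and 79% figures describe an assumed analysis. The omission remains whichever analysis is used.
- **The arithmetic does not measure the defect.** Every input except the sample size is assumed, and 30 per arm is not shown to be inadequate. This stands; the figures carry no weight in judging whether the defect exists.
- **The remedy involves choices.** Requiring success in both stress and rest would be valid too, a one-sided 5% level would need a narrower margin (0.642 SD for 80% power by the normal approximation), and a larger sample could support a tighter margin. All true. Deleting the clause would also leave the constancy and linearity claims without a criterion.
- **Context.** This is a small imaging study of two approved agents, and patient risk is unaffected. Section E.4, which says the study will show Dotarem to be suitable, makes no comparison with gadobutrol and adds little support. But Aim 1 is worded as a hypothesis test within a randomized comparison, and this context does not supply the missing rule.

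**Conclusion.** The concern holds and must be fixed. As written, the plan has no valid route to confirming the non-inferiority hypothesis in Aim 1. This rests on reading sections A, D.1, D.2 and D.3 together, and nothing elsewhere in the document fills the gap.

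The practical size depends on assumptions. With a t-based analysis at two-sided 5%, all 60 patients evaluable and no true difference, the design has 80% power only for a margin of about 0.74 SD. Reading a non-significant result as non-inferior would pass an agent worse by 0.3 SD about 79% of the time, and one worse by 0.5 SD about 52% of the time. Whether a margin near 0.74 SD is acceptable cannot be judged, because the plan gives neither an SD nor a clinically tolerable loss.

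**What to change.** Amend D.3 before any analysis:

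1. Name one per-patient signal parameter, one condition (stress or rest), and the direction that counts as worse.
2. State a margin justified on imaging or clinical grounds, not derived from the sample size. Conclude non-inferiority only if the two-sided 95% CI for Dotarem minus gadobutrol excludes it: by the lower limit if higher values are better, by the upper limit if lower values are better.
3. State that a non-significant difference test is not evidence of non-inferiority.

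If no justifiable margin can be supported with 30 per arm, delete the non-inferiority clause from Aim 1 and report the between-group difference with its 95% CI.

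The cost is wording in D.3 or the loss of one clause, with no extra patients or scans. Keeping the claim with a margin tighter than 30 per arm can support would require a larger sample. The downside of deletion is a more modest claim, and it is the likely outcome if the justified margin is well below about 0.74 SD.
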